6.3.5 Pharmacodynamic Assessments

Throughout the study, following metabolic outcome assessments were performed:

- Hemoglobin A1c (HbA1c) at Visit 1 and Visit 15-19
- Insulin dose adjusted HbA1c (IDAA1c): insulin dose adjusted measurement of glycemic control calculated as:
HbA1c (%) + [4 x insulin dose (IU/Kg/24h)]. The last collected value of insulin dose will be used for Visit 1-13 and the average for the 3 days before each visit will be used for Visit 14-19

Summary statistics, graphs and listings will be given for the PD variables.

In addition summary statistics for insulin dose per body weight (IU/kg) will be shown per visit. For Visit 14-19 the average use the 3 days before the visit will be used.

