6.4.1 Electronic Patient Reported Outcomes (ePRO)

All patients (except for the single dose patients) will be asked to keep an electronic diary. The diaries will contain following information:

Confidentiality Statement

- Safety related information (all experienced adverse events and serious adverse events, including signs of clinical sepsis and known risks associated with the use of anti-CD3 mAb or with T1D glycemic control)
- Occurrence of hypoglycemic events including all relevant information for standard classification (these will be captured separately from other safety related information)
- Deviations from planned study drug intake (e.g. missed doses or incorrect doses taken)
- Changes in concomitant medication intake
- Insulin requirements: Daily

The electronic diaries will be kept from the day of signing the informed consent until the patient is withdrawn or completes the study.

A site research coordinator will train the patients on how to complete the electronic diary.

The research coordinator will review these diaries at every follow-up visit to verify that they have been completed properly and consistently. If needed, the patients will be re-trained on the completion of the diary. All relevant data reported in the diaries will be translated into the eCRF by the research coordinator.

6.4.2Continuous Glucose Monitoring (CGM)

All study patients (except for the single dose patients) will receive a XXX CGM device for the entire duration of their study participation. The investigator will train the patients on how to place the CGM device and will provide written instructions to the patient. The data generated by the device will be downloaded at every site visit. The devices will store data for up to 30 days.

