6.3 Hypotheses and Statistical Methods

6.3.1 Definitions

Baseline Visit 1 is defined as the baseline visit, however if a measurement is retaken at Visit 2 before dosing this will be used as the baseline value instead of the Visit 1 value. This concerns laboratory measurements, vital signs, physical examination and concomitant medication (including insuline use). For fasting glucose baseline is defined as the average of the -10 minute and 0 minute values at screening (Visit 1).

Difference from baseline

The difference from baseline is defined as the difference from the baseline according to the definition above.

Relative day The relative day of an event is derived as:

$$\text{Relative day} = (\text{Start date}) - (\text{Date of first administration of IMP}) + 1$$

For events occurring or starting before the date of first administration of IMP, the relative day is derived as:

$$\text{Relative day} = (\text{Start date}) - (\text{Date of first administration of IMP})$$

In this way, there will be no Day 0. Day 1 is the same day as the day of first administration of IMP, and Day -1 is the day before.

TEAE A TEAE is defined as any adverse event (AE) not present prior to the initiation of the treatment(s) or any AE already present that worsens in either intensity or frequency following exposure to the treatment(s).

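### SAP 6.3.5 takes baseline insulin dose as the last collected value but follow-up dose as a 3-day average, so each IDAA1c change from baseline compares unlike quantities (minor)

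*SAP*

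**What the plan says.** SAP 6.3.5 defines IDAA1c as HbA1c plus four times the daily insulin dose per kg. It gives two rules for the dose: "The last collected value of insulin dose will be used for Visit 1-13 and the average for the 3 days before each visit", the average being for Visits 14-19. The same section schedules "Hemoglobin A1c (HbA1c) at Visit 1 and Visit 15-19". For the separate summary of insulin dose per kg it repeats only the later rule ("For Visit 14-19 the average use the 3 days before the visit will be used") and gives none for Visits 1-13. It gives no reason for the difference and does not say what period a last collected value covers.

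SAP 6.3.1 makes Visit 1 the baseline, but a value retaken at Visit 2 before dosing replaces it. On the scope of that rule it says: "This concerns laboratory measurements, vital signs, physical examination and concomitant medication (including insuline use". Visit 2 still falls under the last-value rule.

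The output list (SAP 7.1, group 14.2) plans change from baseline for HbA1c and IDAA1c. Insulin use per kg appears there only as a per-visit summary, although SAP 6.5 says in general terms that summary tables show changes.

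Protocol 6.4.1 has insulin requirements entered daily in the diary and adds: "The electronic diaries will be kept from the day of signing the informed consent until the patient is withdrawn or completes the study". Protocol 7.3.2 lists a diary review, including insulin use, among the Day 1 procedures before first dosing.

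**The concern.** A change from baseline is easiest to read when both ends are measured the same way. Here the one baseline IDAA1c rests on a different dose measure from all five follow-up values (Visits 15-19). If the last collected value is a single day, each change carries the full day-to-day variation of that day. Because the same baseline is subtracted each time, one atypical day moves a patient's whole IDAA1c trajectory. If it is instead a usual or prescribed dose noted at screening, baseline and follow-up may differ systematically even when nothing has changed.

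Little of this averages out in groups this small: 4 to 6 repeat-dose patients per AG019 cohort, and 10 active and 2 placebo patients per combination cohort (2 open-label active plus 10 randomized 4:1). HbA1c, insulin use and IDAA1c are the only PD variables in this SAP (SAP 3.2), and the study is meant to inform later designs (SAP 4.2), where the observed spread of IDAA1c change could be reused.

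**Working it through.** The plan states no SD, significance level, power or calculated sample size for IDAA1c, so there is no figure of its own to reproduce.

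**Which visits are affected.** Counting the visits in Protocol 7.3 gives 19, as SAP 4.1 states: Visit 1 is screening, Visit 2 is Day 1, Visit 13 is Day 12, Visit 14 is Day 28, Visit 15 is Day 56, and Visits 16-19 are Days 90, 180, 270 and 360. With HbA1c only at Visits 1 and 15-19, the last-value rule reaches exactly one IDAA1c per patient, the baseline.

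**Insulin noise in a change, if the last value is one day's dose.** Let s be the within-patient day-to-day SD of dose, and v the variance of a 3-day mean relative to one day. Days in different windows are taken as independent.

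- As planned: s²(1 + v)
- Matched 3-day means: s²(2v)

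| Correlation of days within a window | v | As planned | Matched | Fall in variance |
|---|---|---|---|---|
| 0 | 1/3 = 0.333 | 1.33s² | 0.67s² | 50% |
| 0.3, equal for all pairs | (1 + 0.6)/3 = 0.533 | 1.53s² | 1.07s² | 30% |
| 0.6, equal for all pairs | (1 + 1.2)/3 = 0.733 | 1.73s² | 1.47s² | 15% |

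For independent days, the correlation of insulin noise between two visits' changes is 1/1.333 = 0.75 as planned and 0.333/0.667 = 0.50 when matched.

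**On the IDAA1c scale.** Dose is multiplied by 4, so for independent days the per-patient noise SD is 4s√1.333 as planned and 4s√0.667 when matched. The values of s are assumptions.

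- s = 0.05 U/kg: 0.23 as planned, 0.16 matched
- s = 0.10 U/kg: 0.46 as planned, 0.33 matched
- s = 0.15 U/kg: 0.69 as planned, 0.49 matched

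For the mean of 2 placebo patients at s = 0.10, this is 0.46/√2 = 0.33 as planned and 0.33/√2 = 0.23 matched.

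**Against the total SD of IDAA1c change.** Take s = 0.10 and an SD of 1.0 from all other sources (both assumptions).

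- Independent days: √(1 + 16 × 0.01 × 1.333) = 1.102 as planned, and √(1 + 16 × 0.01 × 0.667) = 1.052 matched. The planned SD is 4.7% larger.
- First-order autoregressive days with correlation 0.5: v = (3 + 4 × 0.5 + 2 × 0.25)/9 = 0.611. The SDs are √(1 + 0.16 × 1.611) = 1.122 and √(1 + 0.16 × 1.222) = 1.093. The planned SD is 2.6% larger.

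Over s = 0.03 to 0.15 and other SD 0.5 to 1.5, the increase runs from 0.2% to 22% for independent days and from 0.1% to 10% at correlation 0.5.

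**If the last value is a usual or prescribed dose.** The formulas above do not apply. A per-patient discrepancy of d U/kg between that dose and a diary average shifts every IDAA1c change for that patient by 4d. The documents give no basis for a value of d.

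**The case against.** The strongest reply is that the rule may be practical and the consequence small. The diary starts at consent, so no diary average exists before Visit 1, and baseline HbA1c is drawn at that visit. A Day 1 insulin average would be paired with an HbA1c taken up to 28 days earlier. No minimum gap between consent and Day 1 is set; the one week in Protocol 7.3.1 is only an ideal for registering the patient. Protocol 6.4.1 has relevant diary data transferred to the eCRF, which does not guarantee every pre-dose daily dose. Two interim analyses have already been run (SAP 6.9), and a new baseline may not agree with them. IDAA1c is secondary, nothing is tested, and individual values are plotted and listed.

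These points stand as limits and have to be handled in the fix, but they do not remove the mismatch. SAP 6.3.1 already allows a Day 1 insulin value beside a screening HbA1c. Diary insulin is reviewed before dosing on Day 1, and a fallback covers patients with too few days. SAP 6.9 treats the Day 180 primary analysis as still to come.

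A reader might infer that every PD change from baseline is degraded, or that the variance of the change doubles. The documents do not support either. HbA1c change does not involve insulin, no change table is listed for insulin per kg, and the factor of 2 concerns the insulin-noise component alone, for independent days, if the undefined last value is one day's dose. Nor does the mismatch by itself favour active or placebo, since the same rule applies to every group.

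**Conclusion.** The inconsistency is real and confined to IDAA1c change from baseline at Visits 15-19. If the last collected value is one day's dose, a matched baseline cuts insulin-noise variance by half for independent days, and by 30% or 15% at within-window correlations of 0.3 or 0.6. The gain in total SD of IDAA1c change is probably modest, about 3-5% in the middle case. That size depends on the assumed s, correlation and other-source SD, none of which the documents give. If the value is a usual or prescribed dose, the issue is comparability and a possible systematic shift in within-group change, whose direction and size cannot be determined here.

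The primary TEAE endpoint is untouched, and no test or sample size depends on this. Severity is minor: a cheap improvement to a secondary descriptive PD measure.

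**What to change.** In SAP 6.3.5, define baseline insulin dose as the mean of the last 3 available diary days before first dosing on Day 1, falling back to the last collected value if fewer than 3 days exist. Say what period and source the last collected value represents. Use this baseline in baseline IDAA1c and in the baseline IU/kg summary, and state that it is paired with the screening (Visit 1) HbA1c.

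The cost is one or two SAP sentences and some reprogramming, with no new procedures for patients or sites. Before adopting it, confirm that the pre-dose daily doses are in the database. There are two downsides to name. Baseline insulin and HbA1c can be up to 28 days apart, and baseline values may differ from those in the interim outputs already produced. The clinical study report should note the second.

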6.3.3.1 Mixed Meal Tolerance Test

The MMTT is a liquid meal that is ingested in the fasting state with timed measurements. Also this test is meant to assess the potential participant's insulin production capability. This assessment will be conducted within 21 days of randomization (except for the single dose patients) and at predefined follow-up visits as outlined in the visit schedule. In order for the results to be meaningful, it is important for the participant to follow certain dietary and lifestyle guidelines in the days preceding the test. A high carbohydrate diet must be followed for the three days leading up to the test.

The test should be rescheduled if the participant has a blood glucose (measured on his/her home meter) less than 70 mg/dL (3.85 mmol/L) or greater than 200 mg/dL (11.1 mmol/L).

The participant is required to fast starting the night before the test, and is instructed to consume only water for at least ten hours preceding the test. Long-acting insulin or Basal rates (insulin pump users) will continue as normal. The use of rapid-acting insulin is acceptable up to 2 hours before the MMTT and the use of short-acting insulin up to 6 hours before the MMTT to correct hyperglycemia.

Mixed Meal Dose: The test meal (Boost High Protein) is given at a dose of 6 mL per kilogram body weight. Maximum dose is 360 mL. Boost High Protein is supplied in 8 fluid ounce containers. The Sponsor will supply the test meals.

The MMTT takes approximately four hours to complete, and must be scheduled in the morning (i.e. must be started before 10 AM). It is important to carefully review the eligibility criteria with the participant before starting the test, since if certain criteria have been violated the test will need to be rescheduled for another date.

Procedure: Mixed Meal Dose

Step 1. Ensure the patient is currently fasting

Step 2. Prepping Participant for MMTT

- a. The MMTT must begin between 7:00 10:00 a.m. for proper interpretation.
- b. Obtain the weight of the participant and calculate Boost High Protein meal size = 6 mL/kg, up to 360 mL, 1lb = 0.45 kg

Confidentiality Statement

- c. The MMTT test uses a standard oral mixed meal formula (Boost High Protein) composed of liquid sucrose, soy protein, casein, and soy oil. The test meal is given at a dose of 6 kcal/kg body weight, at 1 kcal/mL to a maximum of 360 kcal.
- d. The participant should remain sitting or resting in bed quietly throughout the test.

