Details on collection, labelling and storage of the samples will be explained verbally and in writing to the patients.

A 2-day visit window is allowed for the Day 56 visit. The first feces sample will be collected in the hospital on the Day 56 follow-up visit, regardless on which day this visit takes place. If it is not possible to collect a feces sample at the site, the sample collection equipment will be given to the patient and a sample will be collected at home, ideally on the same day. Subsequent samples will be collected every 2 days following this visit, as described in the below table.

EOT visit date	First sample	Second sample	Third sample	Fourth sample	Fifth sample
D54	D54	D56	D58	D60	D62
D55	D55	D57	D59	D61	D63
D56	D56	D58	D60	D62	D64
D57	D57	D59	D61	D63	D65
D58	D58	D60	D62	D64	D66

Confidentiality Statement

7.3.4Visits after the active treatment phase

7.3.4.1Day 90 follow-up visit

Following observations and procedures will be completed:

- Physical Exam
- Vital Signs
- Urine pregnancy test (in women of childbearing potential)
- Blood sampling for local lab (hematology, chemistry)
- Infectious disease monitoring (PCR)
- Blood sampling for mechanistic assessments (only for repeat dose patients in AG019 Cohorts
 2 and 4 and for patients in the combination cohorts)
- Blood sampling for central lab (HbA1c)
- Blood sample for central lab PK
- Mixed Meal Tolerance Test (MMTT)
- Record concomitant medications
- Record adverse events
- ePRO review including insulin use and hypoglycemic events
- CGM readings/download

7.3.4.2Day 180 follow-up visit

Following observations and procedures will be completed:

- Physical Exam
- Vital Signs
- Urine pregnancy test (in women of childbearing potential)
- Blood sampling for local lab (hematology, chemistry)
- Blood sampling for mechanistic assessments (only for repeat dose patients in AG019 Cohorts
 2 and 4 and for patients in the combination cohorts)
- Blood sampling for central lab (HbA1c)
- Mixed Meal Tolerance Test (MMTT)
- Record concomitant medications
- Record adverse events
- ePRO review including insulin use and hypoglycemic events
- CGM readings/download
- 12-lead ECG (only if there is suspicion of cardiac problems)

7.3.4.3Day 270 follow-up visit

Following observations and procedures will be completed:

- Physical Exam
- Vital Signs
- Urine pregnancy test (in women of childbearing potential)

Confidentiality Statement

- Blood sampling for local lab (hematology, chemistry)

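### When the MMTT is done on the visit day, the 3-day insulin window behind IDAA1c and IU/kg falls on the pre-test high-carbohydrate diet at Days 90, 180 and 360, but not at Days 28, 56 and 270

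*SAP*

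**What the plan says.** SAP 6.3.5 defines IDAA1c as HbA1c (%) plus 4 times the insulin dose per kg per 24 hours. For that dose, "The last collected value of insulin dose will be used for Visit 1-13", and for the later visits "the average for the 3 days before each visit will be used for Visit 14-19". The per-visit IU/kg summary follows the same rule: "For Visit 14-19 the average use the 3 days before the visit will be used". HbA1c, and so IDAA1c, is available as follows: "Hemoglobin A1c (HbA1c) at Visit 1 and Visit 15-19". The output list (SAP 7.1, section 14.2) reports HbA1c and IDAA1c as absolute values and change from baseline, and adds mean and individual plots over time.

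The protocol's Mixed Meal Tolerance Test section (within 6.3.3) states: "A high carbohydrate diet must be followed for the three days leading up to the test". The visit lists in Protocol 7.3 put an MMTT at screening and at Days 90, 180 and 360. The lists for Days 28, 56 and 270 have none. The diary in Protocol 6.4.1 records "Insulin requirements: Daily".

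Neither document mentions that the two three-day periods can coincide, and no alternative window is planned. SAP 6.5 has no covariate adjustment. SAP 6.6 analyses data as they stand, apart from missing dates.

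**The concern.** The insulin average is meant to describe the dose each patient needs around the visit. If it is taken during an imposed diet at some visits and on usual eating at others, the follow-up visits no longer measure the same thing. Patients are treated to pre-meal and post-meal glucose targets (Protocol 5.1.3), so it is plausible that they take more mealtime insulin on a high-carbohydrate diet. Three days of diet would hardly move HbA1c, so nothing in IDAA1c would offset the change in dose.

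Insulin use and IDAA1c are two of the three PD variables that this SAP analyses (SAP 3.2). Day 56 is the end of treatment and Day 180 is the time of the primary analysis, and they fall on opposite sides of the diet pattern. A rise in dose on the diet would look like worsening between Day 56 and Day 90 and improvement at Day 270. The Phase 1b cohorts have no control group to show whether such a pattern comes from disease course or from diet.

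**Working it through.** **No plan figure to reproduce.** The sample size has no statistical basis (Protocol 10.2), and the documents give no usual insulin dose, carbohydrate amount or diet effect.

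**Step 1: visit numbers to study days.** The protocol text gives screening (1 visit), Days 1 to 12 (12 visits) and Days 28, 56, 90, 180, 270 and 360 (6 visits). The sum is 1 + 12 + 6 = 19, the number in SAP 4.1. Visits 14 to 19 are therefore Days 28, 56, 90, 180, 270 and 360. Two SAP lists confirm this:
- ECG at Visits 1, 15 and 19, and at Visit 17 if a cardiac problem is suspected, matches screening, Days 56 and 360, and conditionally Day 180.
- Viral PCR at Visits 13 to 16 and 19 matches Days 12, 28, 56, 90 and 360.

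**Step 2: overlap of the windows.** The insulin window is visit day minus 3 to minus 1. The diet window is MMTT day minus 3 to minus 1.

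| Visit | Day | MMTT listed | IDAA1c available | Diet days in insulin window (MMTT on visit day) |
|---|---|---|---|---|
| 14 | 28 | no | no (IU/kg only) | 0 of 3 |
| 15 | 56 | no | yes | 0 of 3 |
| 16 | 90 | yes | yes | 3 of 3 |
| 17 | 180 | yes | yes | 3 of 3 |
| 18 | 270 | no | yes | 0 of 3 |
| 19 | 360 | yes | yes | 3 of 3 |

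The protocol reschedules the test if home glucose is below 70 or above 200 mg/dL. Counted against the diet for the completed test, the overlap falls to 2, 1 and 0 of 3 days when the test is 1, 2 and 3 or more days after the visit. If the diet had already been followed for the first date, the insulin window can still contain diet days from that attempt.

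**Step 3: effect on the PD variables.** With usual dose D and relative change r on the diet, IU/kg moves by D × r and IDAA1c by 4 × D × r. D and r are assumptions.

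| D (IU/kg/24h) | r | Change in IU/kg | Change in IDAA1c |
|---|---|---|---|
| 0.2 | 5% | 0.01 | 0.04 |
| 0.5 | 10% | 0.05 | 0.20 |
| 0.5 | 20% | 0.10 | 0.40 |
| 0.5 | 30% | 0.15 | 0.60 |
| 0.8 | 30% | 0.24 | 0.96 |

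**Step 4: change from baseline.** SAP 6.3.1 takes baseline insulin at Visit 1, or at Visit 2 before dosing if retaken. Screening also includes an MMTT with its diet, so the baseline value may or may not fall on a diet day. Using the 0.20-point example:

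| Baseline dose taken | Shift in change from baseline, Days 56 and 270 | Days 90, 180 and 360 |
|---|---|---|
| off diet | 0 | +0.20 |
| on diet | −0.20 | 0 |

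In both rows the apparent step is +0.20 from Day 56 to Day 90, −0.20 from Day 180 to Day 270, and +0.20 from Day 270 to Day 360. The baseline condition decides which visits carry the error, and it can differ between patients.

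**The case against.** The strongest case against the point is that only the overlap is documented. The carbohydrate content of the diet is not quantified, and a rise in dose is an inference. A percentage rise in total daily dose also overstates what diet alone can do, because basal insulin does not normally follow meals. If half the dose is basal (an assumption), a 10% total rise needs a 20% rise in mealtime insulin, and a 30% total rise needs 60%. This stands. The upper rows of the Step 3 table should be read as bounds, not as expected values.

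Three stronger readings are tempting, and the documents do not support them:
- **The comparison of active with placebo at Day 180 is biased.** Both arms follow the same diet before the same test, so same-visit contrasts are largely protected. Their weakness is size: 10 patients randomized 4:1 gives 2 on placebo per combination cohort. Days 90, 180 and 360 also share one diet condition and can be compared with each other.
- **The Day 180 change from baseline is inflated.** This needs an off-diet baseline, and the SAP rule does not fix that.
- **The windows always coincide.** They do so in full when the test is on the visit day. Rescheduling changes the overlap for individual patients, which adds variation between patients and does not cure the problem.

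The outputs are also descriptive and secondary, and individual plots would let a reader see a zigzag between visits. That limits the consequence. A plot cannot show whether diet caused the pattern.

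**Conclusion.** The point holds for comparisons across visits. With the MMTT on the visit day, the insulin window is entirely on diet at three of the five follow-up IDAA1c visits and entirely off diet at the other two, as it is at Day 28 for IU/kg. Comparisons of Day 56 or Day 270 with Days 90, 180 and 360 are therefore open to a diet explanation that the SAP cannot exclude. So, possibly, is change from baseline. The exposure is greatest in Phase 1b.

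Confidence is high for the overlap and only moderate for its consequence. The example size, 0.20 IDAA1c points, rests on an assumed 0.5 IU/kg/24h and an assumed 10% rise. Over 0.2 to 0.8 IU/kg/24h and 5% to 30%, the range is 0.04 to 0.96 points. The direction, a higher dose on the diet, is plausible but not documented. The primary endpoint, treatment-emergent adverse events, is not affected. The change is worth making because it costs little, but the study does not depend on it.

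**What to change.** Amend SAP 6.3.5 before the blind is broken for the third interim analysis:

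1. **Follow-up.** Use one prespecified window of diary days that leaves out the three MMTT-diet days. One choice is the mean of days −6 to −4 relative to the MMTT date, or relative to the visit date where no MMTT is scheduled. If a test was attempted and rescheduled, also leave out the diet days before the first attempt.
2. **Baseline.** Replace the last-collected value with an equivalent mean of three pre-dose diary days that excludes the screening MMTT and its diet days. The diary starts at consent, so these days may have to come from between the screening test and Day 1. Moving only the follow-up window could make change from baseline less comparable for patients whose baseline dose falls on the diet.
3. **Scope.** Use the same rule for IDAA1c and IU/kg.
4. **Sensitivity.** Keep the current 3-day window as a sensitivity summary. SAP 6.9 says that two interim analyses have already been performed, and this keeps the results comparable with any that used it.

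The cost is SAP wording and programming, with no change to procedures for patients. There are two downsides. The window lies a few days further from the visit, which is minor next to the weeks that HbA1c reflects. The sponsor must also confirm that these diary days are in the analysis database, because Protocol 6.4.1 says only that relevant diary data are carried into the eCRF.
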